- Baseline Visit 2: Maintenance of Wakefulness Test (MWT; Littner et al., 2005). The potential participant will report to the Center for Clinical Investigation (CCI) at BWH approximately one hour after their usual wake time (UW) on early morning start days. The participant will have their vitals taken and then be instrumented for polysomnography (PSG) and a 40-min MWT will be carried out at UW+ ~2, 4, 6, and 8 hours. Five minutes prior to each nap, a KSS will be administered. In between MWTs, the participant will complete baseline questionnaires [Chronotype questionnaire for Shift-Workers (MCTQ shift, Juda et al., 2013), WPAI-SHP, FOSQ-10, SDS, modified ESS]. A physician will evaluate the participant on the CGI Severity of Illness scale and the participant will self-report on Patient's GI Severity of Illness scale. A breakfast and lunch will be served between MWTs, shortly after the end of a nap. If daytime sleepiness is confirmed (average sleep latency of <20 min on the four MWT naps), the participant is considered to meet the inclusion criteria and the study can start. The participant will take home a wrist activity monitor to wear 24/7, and will be instructed to complete an electronic daily diary containing questions related to wake and sleep patterns. This visit is expected to take 10 hours.
- **Baseline Segment**: Two weeks of activity monitoring and daily completion of a sleep and work diary. Daily sleep surveys will be administered prior to starting work and daily work diaries will be administered after work at participant-selected times and will be sent to participants via email or via text message using Twilio, or provided in a hard-copy binder.
- Randomization Visit 3: The participant will have their wrist activity monitor downloaded and reinitialized, vital signs will be recorded, they will be asked about their symptoms and about any adverse events, and have the C-SSRS-since-last-visit reviewed with them, and female participants will have a urine pregnancy test. If no exclusionary criteria are identified, the participant will be randomized and given their first 2 weeks of study medication.

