the CCI where MWT and KSS will be carried out as at Visit 2. Thus, the first MWT will start approximately 2 hours after taking the study medication. In between MWTs, the participant will complete post-treatment questionnaires [WPAI-SHP, FOSQ-10, SDS, modified ESS]. After the MWT is complete, a PE including vital signs and an EKG will be carried out, and a symptom check and AE review will be done along with a C-SSRS-since-last-visit. A urine sample will be collected for UA and blood will be collected for a CBC and metabolic panel. A physician will evaluate the participant on the CGI-Change to assess changes from baseline in symptom severity and efficacy, and the participant will self-report on Patient's Global Impression of Change.

• **Final Safety Visit 6:** Approximately one week after Visit 5, a final Safety Visit is scheduled including a PE, vital signs, symptoms, AEs, and C-SSRS-since-last-visit.

If a participant drops out after at least 1 week on treatment, they will be encouraged to come in for an MWT (Visit 5).

Drugs to be used.

The administered drug is SUNOSI (solriamfetol) tablets for oral use. Initial U.S. Approval: 2019.

Participants will start at 75 mg and take that dose for 3 consecutive days. Participants will take their first 75mg dose on an early morning work day and take the next two 75 mg doses upon awakening regardless of their work schedule.

They will then move to 150mg on the next early morning work day and for all subsequent early morning shift work days. The drug/placebo will be taken orally within 30 minutes after awakening, before the start of each early morning shift. Prior to the end of study of visit (Visit 5), drug will be taken at home within 30 minutes of awakening.

Devices to be used

No experimental/investigational devices will be used in the study. Several devices will be used to collect screening or research data in the study:

- During screening, an Embletta or equivalent home sleep monitor (battery-operated) will be used to record breathing/leg movements for the overnight HST.
- Throughout the Baseline Segment and the Treatment Segments, a battery-operated wrist activity monitor (MotionWatch 8) will be used to record activity data.
- During the MWT tests carried out at the CCI, a Vitaport 3 sleep recorder will be used to record PSG data.

All these devices are battery-operated, non-invasive, and are currently used in multiple research studies at BWH.

Data to be collected

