Underlying psychiatric comorbidities (ie, affective disorders and suicidal ideation) could be exacerbated by the use of a stimulant or wake-promoting agent. In the solriamfetol clinical development program, serious psychiatric events occurred more commonly in the narcolepsy population than the OSA population. Further, although solriamfetol blocks dopamine and norepinephrine reuptake, nonclinical and clinical data show that the potential for abuse for solriamfetol is low.

Dose-dependent increases in blood pressure (BP) and heart rate (HR) have been seen in clinical studies of solriamfetol in patients with narcolepsy and OSA. This population may be at risk for cardiovascular events due to certain intrinsic factors, such as increasing age, obesity, concurrent diabetes mellitus or cardiovascular disease, hyperlipidemia, and hypertension. In addition, shiftwork may predispose patients to cardiovascular disease. Based on the cardiovascular co-morbidities in this population and depending on the cardiovascular risk profile these events are anticipated to occur in this population.

In previous studies, the most common adverse reactions (incidence ≥ 5% and greater than placebo) reported more frequently with the use of solriamfetol than placebo were headache, nausea, decreased appetite, anxiety, and insomnia

Other risks.

Common

- There may be some discomfort or bruising on collection of the blood samples during the screening and EOT visits. The amount of blood drawn for biochemical screening tests of blood and urine should not significantly alter blood volume.
- The tape and special paste used to attach the EEG electrodes for the MWTs may cause some minor discomfort or skin irritation, and the glue (collodion) used to hold electrodes to the scalp may leave a flaky residue in the hair for several days.
- The adhesive EKG and EMG pads may cause some skin irritation when they are removed.

Uncommon

There is the possibility that the participant may faint during or after the blood draw procedure.

Device complications/malfunctions

The battery-operated monitoring devices are electrically safe and involve minimal risk. The devices used to monitor brain electrical activity (EEG) in the laboratory are battery-operated.

Psychosocial (non-medical risks)

- The daily diaries pose no risks, although they will be repeated many times over the course of the study.

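### Visit 5 vital signs are written only after the last MWT, about 8 hours after dosing, so no scheduled blood pressure covers the earlier post-dose hours and the change from Visit 2 is not like for like

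*Combined protocol and SAP*

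**What the plan says.** Section V, Baseline Visit 2, has the participant arrive "approximately one hour after their usual wake time (UW) on early morning start days". The order of events is then "The participant will have their vitals taken and then be instrumented for polysomnography (PSG", after which "a 40-min MWT will be carried out at UW+ ~2, 4, 6, and 8 hours".

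Section V, End of Treatment Visit 5, has the participant dose at home and travel to "the CCI where MWT and KSS will be carried out as at Visit 2". That cross-reference names the MWT and the KSS, not vital signs. The only vital signs written for the visit follow the naps: "After the MWT is complete, a PE including vital signs and an EKG will be carried out". On dose timing, the visit description says that "the first MWT will start approximately 2 hours after taking the study medication", and Drugs to be used says that before this visit "drug will be taken at home within 30 minutes of awakening".

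Vital signs are also recorded at Visits 3, 4 and 6, and Section VIII (Safety monitoring) asks for them at every visit. None of these entries gives a clock time or a time since dose. Visit 3 precedes the first dose and Visit 6 comes about a week after Visit 5. After the first three treatment days, dosing is on early-morning work days only.

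Section VI (Drug side effects and toxicities) states that "Dose-dependent increases in blood pressure (BP) and heart rate (HR) have been seen in clinical studies of solriamfetol", and adds that shift work may predispose to cardiovascular disease. It gives neither the size nor the time course of the rise. Section V.b names no blood-pressure or heart-rate endpoint and describes no safety analysis.

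**The concern.** Wakefulness is sampled four times across the post-dose day at Visit 5. Blood pressure, a risk that the protocol itself names, is sampled once, at the end of that day. The matching pre-treatment reading was taken in the first hour or so after arrival.

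Two things follow. A clinician or analyst who compares a participant's Visit 5 reading with the Visit 2 reading sees drug effect and time of day added together. And if the rise is larger in the hours soon after the dose, which is the part of the day when participants would normally be at work, the scheduled reading shows only what is left of it. A small difference at Visit 5 could then be read as reassurance about hours that were not measured.

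**Working it through.** **Inputs** (UW = usual wake time)

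| Quantity | Value | Source |
|---|---|---|
| Arrival and vital signs, Visit 2 | about UW + 1 h | Section V, Visit 2 |
| MWT starts, both visits | UW + 2, 4, 6, 8 h | Section V, Visits 2 and 5 |
| Maximum nap length | 40 min = 0.67 h | Section V, Visit 2 |
| Dose, Visit 5 | UW + 0 to 0.5 h | Section V, Drugs to be used |
| Vital signs, Visit 5 | after the fourth nap | Section V, Visit 5 |

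**1. The protocol's own figure.** Dose to first MWT = 2 − 0.5 = 1.5 h to 2 − 0 = 2.0 h. This agrees with the stated interval of about 2 hours, so the inputs are being read as intended.

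**2. Time since dose at the Visit 5 reading.** Earliest, with a late dose and a fourth nap that ends almost at once: 8 − 0.5 = 7.5 h. With a dose on waking and a full fourth nap: 8 + 0.67 − 0 = 8.7 h. The examination follows the nap, so the reading falls at about 7.5 to 8.7 h or later.

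**3. Clock gap from Visit 2.** From 8 − 1 = 7 h to 8.67 − 1 = 7.7 h, or more.

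**4. What each contrast estimates.** Let d be the drug effect at about 8 h and s the time-of-day shift between the two readings. The change from Visit 2 is d + s on solriamfetol and s on placebo, so the difference between arms is d. With an assumed d of 4 mmHg:

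| Assumed s (mmHg) | Change, solriamfetol | Change, placebo | Difference |
|---|---|---|---|
| −3 | 1 | −3 | 4 |
| 0 | 4 | 0 | 4 |
| +3 | 7 | 3 | 4 |
| +6 | 10 | 6 | 4 |

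The within-arm change moves with s. The difference between arms does not.

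**5. How much of a peak effect is left at 8 h.** The documents give no time course, so this is an illustration only. If the effect peaks at time t and then halves every h hours, the share left is 2^(−(8 − t)/h):

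| Assumed peak | h = 3 | h = 4 | h = 6 | h = 8 | h = 12 |
|---|---|---|---|---|---|
| 1 h | 20% | 30% | 45% | 55% | 67% |
| 2 h | 25% | 35% | 50% | 59% | 71% |
| 3 h | 31% | 42% | 56% | 65% | 75% |
| 4 h | 40% | 50% | 63% | 71% | 79% |

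The range is 20% to 79%. With a 2-hour peak, less than half is left only if the half-life is below 6 hours.

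**6. Would an arrival reading at Visit 5 be enough?** It would fall at 1 − 0.5 = 0.5 h to 1 − 0 = 1 h after the dose. It removes the clock gap but leaves the period from about 1 to 8 h uncovered. A reading in the gap after the first nap would fall at about 2 − 0.5 = 1.5 h to 2.67 h or later, and one after the second nap at about 4 − 0.5 = 3.5 h to 4.67 h or later.

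**The case against.** The strongest reply is that the placebo arm follows the same schedule, so randomization removes time of day from the comparison between arms. That stands. What it does not do is recover an effect at hours when nothing was measured: the fair comparison is a comparison at about 8 hours.

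A second reply is that no change in blood pressure from Visit 2 to Visit 5 is a planned analysis, so nothing planned is biased. That is also correct, and the confounding applies only to a change that someone may choose to read. But the absence of any planned blood-pressure summary does not make the one timed reading more informative.

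Third, some relevant data already exist. The MWT recordings in Section V.a include an EKG channel, so heart rate could be derived at about 2 to 8 hours after dosing at matched times in both arms. Section V.b lists medication timing among the diary variables, so time since dose at Visit 4 may be recoverable if the visit time is noted. Both points narrow the gap for heart rate and for Visit 4. Neither supplies a blood pressure in the earlier post-dose hours. Section VIII also has nurses monitoring participants at Visits 2 and 5, but it writes no additional readings.

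A reader might infer that the late reading misses most of the rise. The documents do not support that: without a time course, the illustration runs from most of the effect lost to most of it still present.

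**Conclusion.** The timing mismatch is established from the protocol's own times. Vital signs are taken at about UW + 1 h at Visit 2 but about 8 hours after the dose at Visit 5, a clock gap of about 7 hours or more. No blood pressure is scheduled in the earlier post-dose hours at any visit. Visit 4, the only other in-person visit during treatment before Visit 5, has no set time and may fall on a day without a dose.

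The consequence is limited. The efficacy endpoints and their tests are untouched, and the comparison between arms at Visit 5 is valid for the hour at which it is made. What the trial cannot show is the blood-pressure effect over the earlier post-dose hours, so the rise may be understated by an unknown amount. The 20% to 79% range rests wholly on the assumed peak times (1 to 4 h) and half-lives (3 to 12 h), and the 4 mmHg example is likewise assumed. This is a worthwhile improvement to safety measurement, not an error in a planned analysis.

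**What to change.** - At both Visit 2 and Visit 5, take blood pressure and pulse at the same times relative to usual wake time: on arrival before electrode placement, in at least one gap between naps (for example the gap after the first or second nap), and after the last MWT. Set these by time from waking and not by when a nap ends, because a nap stops early if the participant falls asleep, and that may differ between arms.
- Record clock time and time since last dose with every on-treatment reading, at Visits 4 and 5.
- Add to Section V.b a safety summary giving the difference between arms in systolic pressure, diastolic pressure and heart rate at each matched time, adjusted for the Visit 2 value at that time, with a 95% confidence interval. Heart rate can also be taken from the EKG channel already recorded during each MWT.

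The cost is a few minutes of nursing time at two all-day visits where nurses are already present, a short addition to the visit descriptions, and one extra table. Dosing and the MWT schedule do not change.

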- 24-h actigraphy to assess sleep duration and sleep quality

At baseline and End of Treatment visits (visit 1 & 5):

- Objective sleepiness (MWT)
- Subjective sleepiness (KSS, ESS)
- Clinical global impression (CGI, CGI-S, CGI-C)
- Patient global impression (PGI, PGI-S, PGI-C)
- Work function and daily activity (WPAI-SHP)
- Subjective global functioning (FOSQ-10, SDS)

Analysis of objective sleepiness.

The **Primary Endpoint** of this study is the change in objective sleepiness between the Baseline MWT and the End of Treatment (EOT) MWT [average sleep latency on first 4 scheduled naps]. To test the primary hypothesis, the primary endpoint of the change in MWT from Baseline to EOT between the solriamfetol group and the placebo group will be analyzed using a mixed model repeated measures analysis that will include Baseline MWT, treatment (solriamfetol, placebo), time (as a discrete factor), and treatment by time interaction as fixed effects and participant as a random effect. An unstructured variance-covariance matrix will be used to model the correlation among repeated measurements. The degrees of freedom will be estimated by the Kenward-Roger approximation method. A 2-sided 95% confidence interval (CI) of the mean difference in MWT from Baseline to EOT between solriamfetol and placebo will be constructed.

Analysis of subjective sleepiness and clinical condition.

The **Secondary Endpoints** are:

- a) the change in subjective sleepiness between the Baseline KSS and the EOT KSS [average of the KSS given before the first 4 scheduled naps]
- b) the change in clinical condition between Baseline and EOT as assessed by a physician using the CGI-C.
- c) the change in the patient's subjective report between Baseline and EOT visit as assessed by PGI-C.

To test the secondary objectives, the secondary endpoint of the change in KSS from Baseline to EOT between the solriamfetol group and the placebo group will be analyzed using a mixed model repeated measures analysis that will include Baseline KSS, treatment (solriamfetol, placebo), time (as a discrete factor), and treatment by time interaction as fixed effects and participant as a random effect. An unstructured variance-covariance matrix will be used to model the correlation among repeated measurements. The degrees of freedom will be estimated by the Kenward-Roger approximation method. A 2-sided 95% CI of the mean difference in KSS from Baseline to EOT between solriamfetol and placebo will be constructed.

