For the secondary endpoints of CGI and PGI, change between the treatment group and the placebo group will be analyzed using a chi-square test.

To address the multiplicity issue due to the hypothesis testing on the primary and secondary endpoints, a fixed hierarchical testing sequence will be employed. The familywise type I error rate will be controlled at the 2-sided significance level of 0.05. The testing procedure will be stopped when the p-value of a specific endpoint exceeds the significance level of 0.05. Statistical hypotheses will be tested in the following sequential order:

- 1. the change in objective sleepiness between the Baseline MWT and the End of Treatment (EOT) MWT
- 2. the change in subjective sleepiness between the Baseline KSS and the EOT KSS
- 3. the change in clinical condition between Baseline and EOT as assessed by a physician using the CGI-C
- 4. the change in the patient's subjective report between Baseline and EOT visit as assessed by PGI-C.

The **Exploratory Endpoints** are:

- a) the change in subjective sleepiness between Baseline and EOT visit as assessed by modified ESS.
- b) the change in work function and daily activity between Baseline and EOT visit as assessed by WPAI-SHP
- c) the change in subjective global functioning between Baseline and EOT visit as assessed with FOSQ-10 and SDS.
- d) no change in objective sleep duration or sleep quality assessed by actigraphy-estimated TST and actigraphy-estimated FI, averaged across the 2 Baseline weeks compared to weeks 3+4 of Treatment.

To test the exploratory objectives, we will analyze the change from Baseline to EOT between the solriamfetol group and the placebo group by descriptive statistics, and to analyze the continuous variables using a mixed model with repeated measures analysis that will include baseline measure, treatment (solriamfetol, placebo), time (Baseline, EOT), and treatment by time interaction as fixed effects and participant as a random effect, and to analyze discrete variables using a chi-square test.

All significance tests will be 2-tailed and at p < 0.05 level.

Sample Size Justification

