The sample size estimate for the primary endpoint is based on the results of the study of solriamfetol in patients with OSA (Schweitzer, 2019). With 50 participants per group, we can detect a difference of 5.7 minutes or greater on the MWT with power of 97% (α =0.05, assumed σ =7.2). Sample size estimates for the secondary endpoints are based on the results of the study of modafinil in patients with SWD (Czeisler, 2005). With 50 participants per group, we can detect a difference as small as 0.6 points on the KSS with power of 84% (α =0.05, assumed σ =1), and a difference of 27% or greater in the proportion of patients reporting at least minimal improvement on the CGI-C with 80% power (α =0.05, assumed a placebo proportion at 49%).

The study will randomize 110 individuals and allow for a 10% dropout rate. If a participant drops out after at least 1 week on treatment, they will be encouraged to come in for an MWT visit.

VI. RISKS & DISCOMFORTS

Contraindications

Solriamfetol is contraindicated in patients receiving concomitant treatment with MAOI, or within 14 days following discontinuation of MAOI, because of the risk of hypertensive reaction.

Drug side effects and toxicities

Solriamfetol is an FDA-approved (for excessive daytime sleepiness associated with OSA and narcolepsy) medication with a robust clinical safety database comprised of healthy participants and participants with OSA, narcolepsy, Parkinson's disease, and MDD with a consistent safety profile across conditions. The robust efficacy of solriamfetol has been demonstrated among participants with OSA and narcolepsy including examination of post-hoc analysis of the subgroup of participants on concomitant antidepressants. The risks to participants in this study are expected to be similar to those seen in prior clinical studies that evaluated the effects of 75 mg and 150 mg solriamfetol in OSA and narcolepsy patients, including those on concomitant antidepressants. Current information on the efficacy, pharmacokinetic(s), and safety of solriamfetol is provided in the solriamfetol Investigator's Brochure (IB), the United States Package Insert (USPI) and the Summary of Product Characteristics (SmPC).

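### The repeated-measures model for MWT and KSS is over-specified: there is at most one post-baseline value per participant, so the fittable analysis is ANCOVA, and the matching exploratory model needs the same correction

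*Combined protocol and SAP*

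**What the plan says.** Section V (Data to be collected) places MWT and KSS at Visits 2 and 5. Visit 4 lists neither. A participant who stops after at least one week is encouraged to have an MWT that is itself labelled Visit 5, so it adds no second post-baseline value. The Variables list in V.b calls the baseline visit 1 rather than 2; either way there are two occasions.

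In V.b the primary endpoint uses one number per visit, the "average sleep latency on first 4 scheduled naps". The response is stated: "the primary endpoint of the change in MWT from Baseline to EOT between the solriamfetol group and the placebo group will be analyzed". The model has "Baseline MWT, treatment (solriamfetol, placebo), time (as a discrete factor), and treatment by time interaction as fixed effects and participant as a random effect". The plan adds: "An unstructured variance-covariance matrix will be used to model the correlation among repeated measurements". Degrees of freedom are Kenward-Roger, and a two-sided 95% CI is to be given for the difference between arms in the change.

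The KSS model repeats the form ("Baseline KSS, treatment (solriamfetol, placebo), time (as a discrete factor", and so on). For continuous exploratory endpoints the terms are "baseline measure, treatment (solriamfetol, placebo), time (Baseline, EOT), and treatment by time interaction as fixed effects and participant as a random effect". This is the only place where the levels of time are given.

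On power with 50 per group, the plan says "we can detect a difference of 5.7 minutes or greater on the MWT with power of 97" percent (σ = 7.2) and "we can detect a difference as small as 0.6 points on the KSS with power of 84" percent (σ = 1).

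**The concern.** A repeated-measures model needs at least two response rows per participant to give meaning to a time factor, a treatment-by-time interaction, a participant variance and an unstructured matrix. Here the stated response, change, occurs once. The primary model, which is step 1 of the fixed testing sequence, and the KSS model, which is step 2, therefore cannot be fitted in full as written, and the plan does not say which terms to drop.

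The exploratory paragraph has a different fault. It does create two rows, by making baseline a response, but it keeps baseline as a covariate too. That model can be fitted with a random participant effect, but its standard error can be too small.

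**Working it through.** **1. The plan's own power figures.** Two-sample noncentral t, two-sided 0.05, 50 per group, 98 df; noncentrality = δ / (σ·√(2/50)) = δ / (0.2σ).
- MWT: 5.7 / (0.2 × 7.2) = 3.96, power 97.5% (stated 97%).
- KSS: 0.6 / (0.2 × 1) = 3.00, power 84.4% (stated 84%).

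Both reproduce. The plan does not say whether σ is the SD at a visit or the SD of change.

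**2. MWT and KSS model, change as response.** There is one row per participant and five fixed-effect columns: intercept, baseline, treatment, time, treatment-by-time. Time has one level, so its column equals the intercept; treatment-by-time equals treatment. Rank is 3 of 5. Participant and residual variance enter only as a sum: in a simulated dataset of 100 the log-likelihood was -320.240 for every split tried. The combined treatment contrast is unique. In that dataset it was 5.97, identical to ANCOVA on change and ANCOVA on the EOT value (both 5.97, SE 1.21).

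**3. If the exploratory coding of time (Baseline, EOT) were carried into this model.** The fixed effects have full rank (5 of 5), but the baseline row is predicted by itself. As the slope approaches 1, the residual of that row shrinks to zero. Under an unstructured matrix, each tenfold shrinkage adds 100 × ln 10 = 230 to the log-likelihood for 100 participants. In the simulated data it went from -603 (slope 0) to -142 (0.99) to +549 (0.99999). There is no maximum.

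**4. If time meant the four EOT naps.** The fixed effects have full rank (9 of 9). However, a random participant effect plus an unstructured 4×4 matrix has 11 covariance parameters for 10 distinct elements, and the stated endpoint is the visit average.

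**5. Exploratory model as written.** Assumptions: 50 per arm, complete data, residual variance common to both visits, treatment-by-time tested, and visit SDs and baseline/EOT correlation ρ chosen by me, since the documents give none. The baseline covariate is constant within participant, so the treatment-by-time estimate is the difference in mean change. Its correct variance rests on the within-participant mean square:
- Within MS = Var(change)/2 = (σ₀² + σ₁² − 2ρσ₀σ₁)/2.
- Between MS, given baseline = Var(EOT | baseline)/2 = σ₁²(1 − ρ²)/2.

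With equal SDs the ratio between/within is (1 + ρ)/2, which is below 1. Participant variance is then estimated at zero and the two mean squares are pooled. Pooled/within is about (3 + ρ)/4, so the critical value is in effect 1.96·√((3 + ρ)/4).

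| ρ | pooled/within | effective critical value | type I, approximate | type I, simulated (SD 1 at both visits) |
|---|---|---|---|---|
| 0.3 | 0.825 | 1.78 | 7.5% | 7.6% |
| 0.5 | 0.875 | 1.83 | 6.7% | 6.8% |
| 0.7 | 0.925 | 1.89 | 5.9% | 6.1% |

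With unequal SDs the effect can vanish. For SDs 5 and 8 at ρ = 0.7, within MS is (25 + 64 − 56)/2 = 16.5 and between MS is 64 × 0.51/2 = 16.3, so pooling changes almost nothing. Over SD pairs 5/8, 6/8 and 7.2/7.2 simulated type I error was 5.0 to 7.4%. Across all scenarios participant variance was estimated at zero in 42 to 100% of trials.

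**6. Power under ANCOVA.** Residual SD is σ·√((1 + ρ)/2) if σ is the SD of change (equal visit SDs), or σ·√(1 − ρ²) if σ is the SD at each visit; 97 df.

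| σ taken as | endpoint | ρ 0.3 | ρ 0.5 | ρ 0.7 |
|---|---|---|---|---|
| SD of change | MWT | 99.8% | 99.5% | 98.9% |
| SD of change | KSS | 95.8% | 92.9% | 89.6% |
| SD at each visit | MWT | 98.4% | 99.5% | about 100% |
| SD at each visit | KSS | 87.6% | 92.9% | 98.6% |

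If the EOT SD were 8 (above the plan's 7.2) with ρ = 0.3, the residual SD is 8 × √0.91 = 7.63, noncentrality 5.7/(0.2 × 7.63) = 3.74, and MWT power about 96%.

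**The case against.** The strongest reply is that V.b names the response (change), the baseline covariate, the contrast and its confidence interval. Once the terms that cannot be estimated are set aside, one analysis remains, and it is ANCOVA. A generalized-inverse fit of the five fixed-effect columns returns the ANCOVA contrast and standard error. On this view the fault is surplus wording. For MWT and KSS that stands, and three stronger readings that a reader might infer do not hold.

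- That the primary test cannot be carried out or is biased. The contrast is estimable; only individual coefficients and the variance split are not. The redundant random effect may cause trouble in software, but that is over-specification.
- That the analyst is free to choose between ANCOVA and an unadjusted change-score test, which can give different p-values. The plan lists the baseline value as a fixed effect and that term is estimable, so a change-score test would mean deleting a prespecified covariate. How often the two tests disagree therefore does not measure the harm.
- That the primary likelihood is unbounded. This needs the exploratory paragraph's levels of time, which the primary paragraph does not state.

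The reply does not cover the exploratory model, where dropping aliased terms cures nothing. It is fair to add that those endpoints lie outside the testing sequence, and that the inflation depends on an assumed common residual variance, which the plan does not state.

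**Conclusion.** The point holds as an error of specification. The MWT and KSS model carries time, treatment-by-time, a random participant effect and an unstructured matrix that cannot all be identified with one post-baseline value. This follows from the visit schedule and needs no assumed SD or correlation. The consequence is that the written model is not the one that can be fitted in full; the treatment estimate and its test survive as ANCOVA.

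The numerical consequence is confined to the continuous exploratory endpoints: type I error of about 5 to 7.6% against a nominal 5%, under the assumptions in the working. No sample-size problem follows. ANCOVA meets the stated power under either meaning of the plan's σ, though not unconditionally, as the 96% at an assumed EOT SD of 8 shows. It is worth correcting because the first two steps of the confirmatory sequence should be described by a model that can be run as written.

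**What to change.** For MWT and KSS, state ANCOVA: EOT value (or change) on treatment plus baseline value, with the treatment coefficient and its two-sided 95% CI as the test. Delete time, treatment-by-time, the random participant effect, the unstructured matrix and Kenward-Roger.

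Alternatively, state a constrained two-visit longitudinal model: both visits as responses, a common baseline mean, an unstructured 2×2 covariance, no baseline covariate and no extra random effect, with the EOT contrast named as the test.

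Apply the same choice to the continuous exploratory endpoints. Say in the sample-size section which SD σ is. Neither change settles missing EOT values, which need their own rule: with no intermediate MWT or KSS, the present model could not draw on one either.

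The cost is rewording two paragraphs for MWT and KSS and one for the exploratory endpoints before the blind is broken. No new data and no change in sample size are needed.
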